### **6.4 Responsibilities**

#### Principal Investigator (PI):

Checking whether participants report AEs when they are reassessed at 2 and 6 months.

1. Using medical judgement in assigning seriousness and causality.
2. Ensuring that all SAEs are recorded and reported to the sponsor within 24 hours of becoming aware of the event and provide further follow-up information as soon as available. Ensuring that SAEs are chased with Sponsor if a record of receipt is not received within 2 working days of initial reporting.

#### Chief Investigator (CI) / delegate:

1. Clinical oversight of the safety of patients participating in the trial, including an ongoing review of the risk / benefit.
2. Using medical judgement in assigning the SAEs seriousness and causality where it has not been possible to obtain local medical assessment.
3. Review of specific SAEs in accordance with the trial risk assessment and protocol as detailed in the Trial Monitoring Plan.
4. Assigning Medical Dictionary for Regulatory Activities (MedDRA) or Body System coding to all SAEs.
5. Reporting safety information to the Trial Steering Committee (TSC).

#### Sponsor:

1. Central data collection and verification of AEs and SAEs according to the trial protocol onto a database.
2. Reporting safety information to the CI, delegate or independent clinical reviewer for the ongoing assessment of the risk / benefit according to the Trial Monitoring Plan.

#### Trial Steering Committee (TSC):

In accordance with the Trial Terms of Reference for the TSC, periodically reviewing safety data to determine patterns and trends of events, or to identify safety issues, which would not be apparent on an individual case basis.

## **6.5 Notification of deaths**

All deaths will be reported to the sponsor irrespective of whether the death is related to disease progression, the intervention, or an unrelated event. This report will be sent to the sponsor at [contact] within 24 hours of the study team being aware.

## **6.6 Reporting urgent safety measures**

If any urgent safety measures are taken the CI/Sponsor shall immediately and in any event no later than 3 days from the date the measures are taken, give written notice to the REC of the measures taken and the circumstances giving rise to those measures.

# **7 STATISTICS AND DATA ANALYSIS**

The analysis of this trial will be mainly descriptive focusing on estimation rather than hypothesis testing. All baseline measures and outcomes will be summarised for each allocated group using the appropriate descriptive statistics and presented with their associated confidence intervals. No formal comparison of groups will take place. A Statistical Analysis Plan will be developed, setting out the details of all analyses and assumptions for the stage 3 pilot trial before the last patient is recruited.

## **7.1 Sample size calculation**

Stage 3 represents a pilot trial so the effectiveness of the intervention is not being evaluated, therefore a formal power calculation is not appropriate. The sample size is based on a 95% confidence interval approach. For each of the expected proportions/means in the key objectives below, the precision to which we would be able to estimate the proportion/mean given this sample size is presented (nQuery and nTerim v4.0).

For the specific pilot trial objectives, the following are descriptions of the precision of our estimates with the stated assumptions:

i. *Recruitment rate*: It is estimated that the percentage of those approached who are randomised is around 30% therefore the approached sample size will be approximately 387 resulting in a half width for the confidence interval of 5%. The widest confidence interval for this approximation results when the percentage of randomised to approached is around 70% giving an approached sample size of 166 and a 95% confidence interval half width of 7%.

ii. *Acceptability and uptake of the intervention*: it is estimated that the uptake rate across those randomised to the intervention will be 90%, with 58 available participants for this estimation; this would result in a confidence interval half width of 8%.

iii. *Number of participants assessed at 6-months*: It is estimated that the dropout rate from the trial will be 20% of those randomised. With 116 participants randomised into the trial this would result in a confidence interval half width of 7% for the estimate of the dropout rate. Even when considering the statistical worst-case scenario of 50% the resulting confidence interval for this sample size has a half width of 9%.

iv. *Mean asthma related quality of life at 6 months in the control group*: with an estimated standard deviation of 1.4 from the UBIOPRED cohort (1), if data from 46 participants are available at 6 months and therefore

available for this estimation, this would give a confidence interval half width of 0.4 units approximately 0.3 standard deviations.

v. *Completeness of data for asthma related quality of life and healthcare utilisation data across the study in the two groups:* this is estimated at 95% across those randomised and still in the trial at 6 months, giving 92 participants available for this estimation therefore giving a confidence interval half width of 5%. Additionally, we plan to interview 10-20 participants in each intervention group.

## 7.2 Planned recruitment rate

The recruitment target for this study is 116 participants, or 58 per arm. It is planned that recruitment occurs at University Hospital Southampton, St Mary's Hospital Isle of Wight and eighteen other hospitals in England. Each site will be expected to recruit up to 5 participants over a 3 month period with the balance being recruited by University Hospital Southampton and St Mary's Hospital using 20 primary PIC sites.

## 7.3 Primary outcome analysis

As this stage 3 protocol outlines a pilot stage for a definitive phase-3 trial, the primary outcomes will be related to feasibility. All patients will be analysed as randomised (intention-to-treat). Feasibility outcomes include:

- i. Assessing the recruitment rate by presenting the proportion of participants recruited among those approached;
- ii. Assessing the acceptability, uptake and use of the intervention, by presenting the proportion of intervention patients who use the intervention website, in conjunction with findings from qualitative data collection;
- iii. Estimating the follow-up rate at the 6-month assessment (additionally, looking at relative rates for participants recruited from primary care, secondary care, Asthma UK, social media, professional networks and snowballing);
- iv. To monitor the change in and estimate the variance of asthma-related quality of life and asthma control in each group;
- v. To determine if data collection methods for process, effectiveness and cost-effectiveness endpoints are appropriate for this population by assessment of completeness of data at 2 and 6-month assessments;
- vi. To determine whether the PedsQL Asthma Module (with and without the additional emotion questions) and the Paediatric Asthma Quality of Life Questionnaire provide similar information by estimating their pairwise correlation.
- vii. To assess the relative uptake and quality of qualitative data collection from participants via in-person, video or telephone interviews;

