### 5.5.1 Recruitment and identification

[figure not shown]
Adolescent with asthma will be recruited in a number of ways:

- 20 secondary clinics in Southampton, Isle of Wight and other centres:
  - (i) database search by NHS staff with invitation letters; invitation letters will be sent; letter will invite interested adolescents;
  - (ii) opportunistically via posters in clinics and clinic staff mentioning to potential participants; poster will invite interested adolescents.
- Up to 20 local primary care clinics (general practitioner, primary care nurses and community nurses) who will be study participant identification centres (PICs):
  - (i) primary care staff will perform a database search; invitation letters will be sent; letter will invite interested adolescents;
  - (ii) opportunistically via posters in surgeries and primary care staff mentioning to potential participants; poster will invite interested adolescents.
- Asthma UK – advert in newsletters, on website and social media inviting interested adolescents.
- Social media (eg Twitter, Instagram, Facebook) adverts and flyers - those interested will click a button/link which opens the BREATHE4T study website where they can leave their details for the study team to contact them.
- Professional networks (eg respiratory and paediatric physio teams informing patients of the study)
- Snowballing
- Posters, adverts and flyers in various local locations (examples include GP surgeries, chemists, supermarket notice boards, schools, colleges, leisure and sport clubs, coffee shops, asthma support groups and charities (e.g. No Limits), local newspapers)
- Press release

This approach will mean that we will not be able to identify the total number of potential participants who would have seen information about the trial and we will not have information about their basic demographics nor asthma status.

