#### *Via website*

Parents and potential participants will be directed to the trial home page where they will be taken through informed consent/assent process. Informed consent/assent will be obtained prior to the participant undergoing any study activities. This process will involve:

- presentation of the approved information on the web pages (also available in printable leaflet form)
- information will cover the nature and objectives of the study and possible risks associated with their participation;
- participants and/or their parents will be informed that they are able to withdraw from the trial at anytime without giving reasons and without prejudicing his/her further treatment, explanation will be given about the right to withdraw permission to use previously collected data;
- an opportunity for potential participants and/or their parent/guardian to ask questions before signing consent/assent by sending a message to the trial team;
- contact point where the participant /parent or guardian may obtain further information about the trial from the research team.

For younger participants (12-14 years), when the parent consents, an invitation will be sent via email to the adolescent participant. This will take them through a similar but age appropriate assent process. Older participants (15-17 years) will be able to give their own consent to participate and will be given immediate access to the study.

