### 5.5.3 Screening

Questions on the trial web site will assess their eligibility for the trial (age 12-17 years, physician diagnosed asthma, under the care of a general practitioner, community or hospital practitioner for their asthma, no co-existent respiratory conditions and not used breathing techniques).

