## 13.2 Appendix 2 – baseline data questionnaire

1. How old are you?   years

2. Are you male or female? Please circle one: **Male**      **Female**      **Prefer not to say**

3. Which professionals do you see about your asthma? Please circle all that apply.

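### The recruitment rate in section 7.3(i) pools counted and open routes without defining 'approached', and its 5% and 7% half-widths hold only if all 116 participants come from counted approaches

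*Combined protocol and SAP*

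**What the plan says.** Section 7.3(i), the first of the feasibility outcomes, is "Assessing the recruitment rate by presenting the proportion of participants recruited among those approached". Section 7.1(i) gives the precision: it estimates that "the percentage of those approached who are randomised is around 30% therefore the approached sample size will be approximately 387", with a 95% half-width of 5%. It names 70% as the widest case, with 166 approached and a half-width of 7%.

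Section 5.5.1 lists the routes. Some can be counted: letters after database searches in hospitals and in primary care, and direct mentions by staff if someone records them. Others involve no individual approach: Asthma UK adverts, social media, community posters and flyers, snowballing and a press release. The two kinds also occur together inside the clinics, where hospital recruitment includes "opportunistically via posters in clinics and clinic staff mentioning to potential participants; poster will invite interested adolescents"; primary care has a matching entry. Section 5.5.1 then says that "we will not be able to identify the total number of potential participants who would have seen information about the trial".

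Section 7.2 describes recruitment by site: "Each site will be expected to recruit up to 5 participants over a 3 month period", with Southampton and St Mary's supplying the balance through 20 primary care identification centres. Section 7.3(iii) plans to break the follow-up rate down by route, in six categories. Section 7.3(i) has no such breakdown. Section 7 promises a separate SAP, due before the last patient is recruited.

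**The concern.** A proportion needs a denominator that can be counted and a numerator drawn from it. Someone who answers a poster or a social media advert has not been approached in the sense in which a letter recipient has. If such people count as approached once they make contact, their denominator consists of people who had already shown interest, and pooling them with letter recipients averages two different rates. If they do not count as approached but are still counted as recruited, the rate is too high. The plan does not say which applies.

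This matters because the pilot exists to plan a larger trial. Recruitment rate is objective (i), and section 2 puts it first among the items the pilot is to supply for a definitive trial expected to need 300-400 participants. A pooled rate transfers only if that trial uses the same routes in the same proportions. A rate by route can be applied to a different mix. The per-site figure in section 7.2 is a useful benchmark, but it gives recruits per site and not yield per invitation.

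**Working it through.** **Inputs.** N = 116 randomised (sections 7.1 and 7.2); assumed rates p = 30% and 70% (section 7.1(i)); 95% confidence, so z = 1.96. The share f of the 116 who come from counted routes is not in the documents, so the values below are assumptions.

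**1. The plan's own figures.** Number approached n = N/p; half-width h = 1.96 × √(p(1−p)/n).
- p = 0.30: n = 116/0.30 = 386.7, or 387; h = 1.96 × √(0.21/387) = 4.6 points (stated 5%).
- p = 0.70: n = 116/0.70 = 165.7, or 166; h = 1.96 × √(0.21/166) = 7.0 points (stated 7%).
- With n tied to 116/p, h is largest at p = 2/3 (7.0 points), so 'around 70%' as the widest case is also right.

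Both denominators equal 116/p, so the calculation places every participant in the approached pool.

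**2. Precision when only a share f comes from counted routes.** Counted recruits = 116f and n = 116f/p, with h as above.

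| f (assumed) | Counted recruits | n at 30% | h at 30% | n at 70% | h at 70% |
|---|---|---|---|---|---|
| 100% | 116 | 387 | 4.6 | 166 | 7.0 |
| 90% | 104 | 348 | 4.8 | 149 | 7.4 |
| 75% | 87 | 290 | 5.3 | 124 | 8.1 |
| 50% | 58 | 193 | 6.5 | 83 | 9.9 |

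**3. What an unmatched rate would show.** If all 116 were set over counted invitations only, the reported rate would be 116/(116f/p) = p/f. A true 30% per invitation would appear as 0.30/0.90 = 33%, 0.30/0.75 = 40% or 0.30/0.50 = 60%. At f = 75% the 10-point excess is twice the stated 5-point half-width, whereas the loss of precision is under one point (4.6 to 5.3). A mismatch would therefore do more harm than the wider interval.

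**4. Does site-based recruitment settle it?** Under section 7.2 the eighteen other hospitals supply at most 18 × 5 = 90, leaving at least 116 − 90 = 26 for Southampton and St Mary's. Section 5.5.1 puts posters inside hospital clinics and surgeries, so a participant credited to a site may still have had no individual invitation.

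**The case against.** The strongest reply is that the wording already protects the estimate. Both 7.1(i) and 7.3(i) describe a proportion of those approached, so read literally the numerator is a subset of the denominator and a poster recruit who was never approached is in neither. A reader might infer that the plan builds in an inflated rate. It does not: no passage tells the analyst to put all 116 over letters sent. Inflation is a risk left open by the missing definition. The literal reading has its own difficulty, however, because 7.1(i) obtains its denominators by treating all 116 as approached.

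A reader might also infer that recruitment route is not recorded, because the baseline questionnaire in Appendix 2 has no item on it; its nearest question is "Which professionals do you see about your asthma? Please circle all that apply", which concerns care and not recruitment. The documents do not support that inference. Section 7.3(iii) needs route for its follow-up breakdown and so presupposes that it is captured, and Appendix 2 need not be the only record the website keeps.

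Nor does the admission in section 5.5.1 mean that no recruitment rate can be calculated. It concerns how many people saw information about the trial, not how many were invited, so a rate over counted invitations is feasible.

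Three further points stand. Figures 2 and 3 are not shown and might carry counts of people invited. The later SAP could supply a definition, and letters would ordinarily leave records; but verbal invitations not logged at the time cannot be rebuilt afterwards. The analysis is descriptive with no progression threshold, so no decision rule in this trial is affected.

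**Conclusion.** The point holds as a fault of definition and matching, and should be fixed. The arithmetic in 7.1(i) is right. What is missing from the visible text is a definition of 'approached' and a split of 7.3(i) by route, in a plan that mixes countable and open recruitment. As written, 7.3(i) yields one figure that either combines unlike denominators or has none for some recruits, and that figure cannot be applied to a definitive trial with a different mix of routes.

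The stated half-widths require all 116 to come from counted approaches. Otherwise they widen modestly: at 75% counted, 5.3% (which still rounds to 5%) and 8.1%; at 50%, 6.5% and 9.9%. The size of any inflation is unknown because the documents give no open-route share, so the 33%, 40% and 60% above are illustrations and not predictions. The harm falls on planning the definitive trial.

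**What to change.** Amend the protocol before the first invitation, or as early in recruitment as possible:

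- **(a) Define and log.** In 7.1(i) and 7.3(i), define 'approached' as individually invited people: letters sent plus direct staff invitations. Log these by route from the first invitation. Treat any route whose invitations are not fully logged as an open route.
- **(b) Match.** Compute the 7.3(i) proportion and its confidence interval only from routes with counted approaches, taking numerator and denominator from the same routes. Report it by route with the 7.3(iii) categories, extended to cover community posters and the press release, which that list lacks.
- **(c) Open routes.** Report counts at each stage: details left or contact made; consented or assented; passed the website screening questions; met the quality-of-life criterion (<85); randomised. This follows the protocol's own order for website entry, where "Informed consent/assent will be obtained prior to the participant undergoing any study activities" and then "Questions on the trial web site will assess their eligibility for the trial". The quality-of-life step needs its own line because the screening questions in 5.5.3 omit that criterion and Appendix 1 schedules the quality-of-life questionnaires at baseline.
- **(d) Precision.** State in 7.1(i) that 5% and 7% hold only if all 116 come from counted routes, and show the range under assumed shares (5.3% and 8.1% at 75%; 6.5% and 9.9% at 50%).

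**Cost.** Some rewording and a short invitation log. At the plan's own 30%, a hospital recruiting 5 would log about 5/0.30 = 17 invitations over 3 months. Southampton, St Mary's and their identification centres together would log about 26/0.30 = 87 for a balance of 26, and more if letters go out widely. Website consent, screening answers and randomisation already pass through the website, so most of (c) needs no new collection. The downside is that the approach-based rate will cover only part of the sample, with a somewhat wider interval.

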## 7.4 Secondary outcome analysis

There are no planned secondary outcome analyses.

## 7.5 Subgroup analyses

Younger (12-14 years) verses older (15-17 years) adolescents

Male verses female adolescents

## **7.6 Adjusted analysis**

There are no planned adjustments in the analyses described above. Responses to the PedsQL Asthma Module and Paediatric Asthma Quality of Life Questionnaire will be transformed into summary scores using questionnaire-specific published methodology.

## **7.6 Interim analysis and criteria for the premature termination of the trial**

There are no planned interim analyses or specified stopping rules.

## **7.7 Participant population**

The trial analysis will include all participants randomised into the trial, regardless of whether they received the intervention. In addition, an analysis will be undertaken on the protocol-compliant population who will be defined as those who have covered at least half of the training sessions in the online website.

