## 5.2 Trial design

The pilot trial will aim to assess the acceptability, uptake and success in collecting follow up data and variance in asthma-related outcome measures. A parallel group design will be used with participants being randomised to intervention or normal management. The intervention will be a self-guided, breathing retraining digital intervention, delivered via a mobile-friendly, online platform. The intervention will continue to be used for 6 months after which both groups will be reassessed. The usual management control group will then have access to the intervention (delayed access).

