#### **5.5.4 The randomisation scheme**

Participants will be randomised via the study website to the next treatment allocation in the randomisation sequence by the trial team. The list will be generated using block randomisation with variable block sizes with a 1:1 allocation ratio between the intervention and usual management. Those randomised to the intervention will have immediate access to the intervention pages. The control group will be able to access the full intervention website at the end of the trial. The website will alert the study team to a new randomisation by email.

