#### **5.5.5 Blinding**

This is an open trial. It will not be possible to blind the breathing retraining intervention. Control participants will also gain access to the full intervention website once they have finished participating in the trial.

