#### **5.5.8 Long term follow-up assessments**

Participants will be re-assessed after 2 and 6 months. They will be contacted by email with a link to the study website. Instructions on the website will take them through:

- PedsQL Asthma Module
- Asthma control test
- Asthma healthcare utilisation questionnaire

These are the questionnaires they completed at baseline. Additionally, participants in the intervention arm will be asked whether or not they have used the breathing exercises.

Participants will receive two email/text reminders.

Additionally, they will complete the paediatric asthma quality of life questionnaire on paper after 2 and 6 months. This will either be at a face to face visit, will be posted to the study team, returned via email or completed over the telephone.

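### Does the section 7.7 protocol-compliant population need a date and an arm before it can be used?

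*Combined protocol and SAP*

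**What the plan says.** Section 7.7 makes all randomised participants the analysis population, whether or not they received the intervention. It then adds a second analysis on the "protocol-compliant population who will be defined as those who have covered at least half of the training sessions in the online website". Section 5.5.11 says the programme has 8 sessions. No other section defines this set.

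On timing, section 5.5.8 states: "Participants will be re-assessed after 2 and 6 months". Appendix 1 gives windows of 2 to 3 months and 5 to 8 months for these assessments. Section 5.2 states: "The intervention will continue to be used for 6 months after which both groups will be reassessed".

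On control access, section 5.5.5 states: "Control participants will also gain access to the full intervention website once they have finished participating in the trial". Section 5.5.4 puts it slightly differently: "The control group will be able to access the full intervention website at the end of the trial". Appendix 1 marks the web intervention as being for the intervention arm only.

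On reporting, section 7 states: "All baseline measures and outcomes will be summarised for each allocated group using the appropriate descriptive statistics". It describes the analysis as mainly descriptive, rules out formal comparison of the groups, and promises a separate Statistical Analysis Plan before the last patient is recruited. Section 7.3(iv) reads: "To monitor the change in and estimate the variance of asthma-related quality of life and asthma control in each group". The list containing that item is introduced by a statement that patients are analysed by intention to treat.

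**The concern.** A compliance set defined by behaviour during follow-up should normally say when that behaviour is counted. Section 7.7 sets a number of sessions but no date. If the set is used to summarise 2-month outcomes, a participant can belong to it because of sessions done later. The summary would then describe people who went on to engage, not people who had already done the exercises. That could mislead the team designing the definitive trial about early response among users.

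The missing arm raises two further questions. Read literally, a control who does four sessions after being given delayed access also meets the definition, although all of that control's outcomes came before any exposure. If instead sessions stop counting at the 6-month assessment, the set has no controls, and summaries by allocated group appear to lack one of their groups.

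**Working it through.** **The plan's own figures.** No stated figure uses the compliant set. The nearest is the precision for uptake in section 7.1(ii), 90% of 58 participants:

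1.96 × √(0.90 × 0.10 / 58) = 0.077, which agrees with the stated 8%.

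The control-group mean in section 7.1(iv), with SD 1.4 and n = 46, gives 1.96 × 1.4 / √46 = 0.40, which agrees with the stated 0.4. Both figures stay the same however section 7.7 is read.

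**Threshold.** Half of 8 sessions is 4. A count cut-off therefore exists; what is missing is a time cut-off.

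**Timing in the intervention arm.**
- Months of use after the nominal 2-month assessment: 6 − 2 = 4 of 6.
- At the late end of the 2-month window: 6 − 3 = 3 of 6.

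These are lengths of time, not numbers of participants. The documents give neither the share expected to reach session 4 nor when they would reach it. As an illustration only, assume that 50% or 90% of the 58 become compliant, and that 10% to 50% of those do so after the 2-month assessment:

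| Assumed compliant share | Members of the set | Reaching session 4 after the 2-month assessment |
|---|---|---|
| 50% | 58 × 0.50 = 29 | 29 × 0.10 to 29 × 0.50, about 3 to 15 |
| 90% | 58 × 0.90 = 52 | 52 × 0.10 to 52 × 0.50, about 5 to 26 |

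The effect on a 2-month summary could be small or considerable. It arises only if such a summary is produced on this set, and section 7.7 names neither a visit nor an outcome. Classifying compliance once over the 6-month period of use in section 5.2 is an equally coherent reading. For 6-month outcomes in the intervention arm that reading raises no difficulty.

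**Controls qualifying late.** Assume that all sites recruit over the same 3 months, which section 7.2 does not state. The first control could then have access for (3 + 6) − 6 = 3 months before the last participant's final assessment, or (3 + 8) − 5 = 6 months at the window limits. That use comes after the control's participation has ended under section 5.5.5, and no section says it is recorded as trial data. If the end of the trial in section 5.5.4 means the end of the whole study, and section 11.1 means the same when it places the analysis there, the overlap largely disappears.

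**No controls in the set.** Controls with any session before their own 6-month assessment: 0 of 58. A set defined by use of a website that controls cannot open has no control members. Reporting it by allocated group then means reporting the intervention arm. Section 7.3(iv) belongs to the intention-to-treat analysis, which keeps both arms.

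**The case for a change.** The best argument for a change is that section 7.7 commits the team to this analysis, and even a descriptive summary needs a definition under which two analysts would select the same people. Reading the set as intervention-arm only settles both questions about controls but leaves the 2-month timing open. Counting sessions up to each assessment also needs dated session records, and the protocol does not say these exist. If they do not, the problem could come to light too late. Uptake and use of the website are feasibility outcomes in section 7.3(ii), so the number reaching 4 sessions by each assessment would be useful in planning the definitive trial.

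Some of this stands. The date and the meaning of having done a session are unstated, and the Statistical Analysis Plan should give both, whichever reading it adopts. But section 7 assigns the details of all analyses to that document, with a deadline before recruitment ends, so the commitment to fill the gap is already in place. Building a separate set for each visit is a design choice with its own drawback: the 2-month and 6-month summaries would describe different people. Reporting the proportion reaching 4 sessions at each assessment is a helpful extra, not the repair of an error.

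**Conclusion.** No change to the plan follows. Section 7.7 leaves out a time cut-off, an arm and a definition of session completion. The only consequence of substance is that a 2-month summary on this set, if one is made, could include people who became compliant later. The number is unknown; under the assumed shares above it runs from about 3 of 29 to about 26 of 52. The all-randomised analysis, the precision figures in section 7.1, the feasibility outcomes and the intervention arm's 6-month results do not depend on how the gap is filled. The absence of controls is what an adherence subset looks like, and it does not conflict with sections 7 or 7.3(iv).

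This conclusion rests on two assumptions: that analysts treat the set as a descriptive subset of the intervention arm, and that the promised Statistical Analysis Plan states when sessions are counted if 2-month outcomes are summarised on it. Both are ordinary practice. If the second failed, the harm would be confined to one supplementary description.
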